3.3 TYPICAL STUDY CALENDAR*

Procedure	Screening	Pre-operative evaluation prior to receiving LUMI beads treatment	Treatment	Post Treatment	Follow up
		Day 0 to discharge or until off treatment ^b		Within 2 months post treatment	Any time point up to 12 months from initial treatment
Procedures performed by the Referring/ Primary Team					
Evaluation to determine if patient is eligible for TAE	X				
H&P to include baseline symptoms, concomitant medications, etc.	X				
Labs	X				
Procedures performed by the Research Study Team					
Consent	X				
Review of Radiological Assessments ^a	X	X	X	X	X
Review of H&P, labs, and concomitant meds		X			
TAE (if appropriate may include thermal ablation)			X	X ^c	X ^c
Response Evaluation			X	X	X
Adverse Events			X	X ^d	X ^d

^a CT/ CBCT, MRI, or PET scan. All radiological imaging to be performed as clinically indicated and based on the status of the patient.

^b Off treatment is 72 hours post TAE.

^c Patient may require repeat procedures

^d See section 4.1.4 for AE data collection and management during the follow up period.

* Primary teams determine course of follow up, but usually request treating Interventional Radiologist input.

Abbreviated Title: RFA + TACE with RO Beads

Version Date: 04/13/2018

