4 DATA COLLECTION AND EVALUATION

4.1 DATA COLLECTION

All data will be kept secure. The PI will be responsible for overseeing entry of data into an in-house password protected electronic system and ensuring data accuracy, consistency and timeliness. The principal investigator, associate investigators/research nurses and/or a contracted data manager will assist with the data management efforts. All human subjects personally identifiable information (PII) as defined in accordance to the Health Insurance Portability and Accountability Act, eligibility and consent verification will be recorded. Primary data obtained during the conduct of the protocol will be kept in secure network drives or in approved alternative sites that comply with NIH security standards. Primary and final analyzed data will have identifiers so that research data can be attributed to an individual human subject participant.

All AEs, including clinically significant abnormal findings on laboratory evaluations, regardless of severity, will be followed for 30 days or until return to baseline or stabilization of event.

Abbreviated Title: RFA + TACE with RO Beads

Version Date: 04/13/2018

Serious adverse events that occur more than 30 days after the last administration of investigational agent/intervention and have an attribution of at least possibly related to the agent/intervention should be recorded and reported.

An abnormal laboratory value will be considered an AE if the laboratory abnormality is characterized by any of the following:

- Results in discontinuation from the study
- Is associated with clinical signs or symptoms
- Requires treatment or any other therapeutic intervention
- Is associated with death or another serious adverse event, including hospitalization.
- Is judged by the Investigator to be of significant clinical impact
- If any abnormal laboratory result is considered clinically significant, the investigator will provide details about the action taken with respect to the test drug and about the patient's outcome.

End of study procedures: Data will be stored according to HHS and FDA regulations, and NIH Intramural Records Retention Schedule as applicable.

Loss or destruction of data: Should we become aware that a major breach in our plan to protect subject confidentiality and trial data has occurred, the IRB will be notified.

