4.1.2 On Study Data Collection

We will also document bead visibility data during embolization. This information will be collected using a qualitative particle visibility scale by applying a 3-point scale: 0, definitely not visible; 1, probably visible; and 2, definitely visible [21].

Intra-procedural, post treatment, and follow up images will all be saved and stored in PACS. Patient images will be anonymized prior to transfer to a secure work station for analysis. CRF's and non-image data will be stored in the DRD shared drive which has limited access. The DRD shared drive is backed up and managed by the NIH DCRI in keeping with the protection and confidentiality guideline of the Privacy Act of 1974.

Any grade 3 events and higher occurring up to 72 hours post treatment (either with combined RFA and TAE or with TAE alone) will be collected and recorded in the study database as adverse events, except those listed in the Exclusions to Adverse Event Data Collection section (see Section 4.1.3). Grade 2 events will be collected and recorded if not resolved before the patient is considered off treatment (72 hours post treatment). Grade 1 events will not be collected or reported.

Abbreviated Title: RFA + TACE with RO Beads

Version Date: 04/13/2018

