4.3 RESPONSE CRITERIA

4.3.1 Definitions

- Evaluable for bead visibility: All patient imaging will be evaluated for the visibility of the LC LUMI beads using a 3 point scale: 0, definitely not visible; 1, probably visible; and 2, definitely visible as defined the treating interventional radiologists. Other characteristics may be noted such as the radiopacity of the beads, visibility of the beads in the tumor, overall location of beads in relation to the tumor or targeted site.
- Evaluable for toxicity: All patients will be evaluable for toxicity from the time of their treatment with LC LUMI radiopaque beads up to 72 hours post completion of treatment. Grade 3 or greater adverse events, including allergic reactions, collected during this time period, will be followed until resolution. Expected or anticipated adverse events from the research or the study device will not be collected. See Section **4.1.3** for details.
- Evaluable for imaging characteristics: Only those patients who are eligible for the study, have received at least one treatment of TAE, and have had their disease re-evaluated per standard of care imaging will be considered evaluable.

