		
observation period)
 
 • Abdominal visceral injury (from non-target embolization, 1-2 weeks following embolization): 		
of misembolization.
 
Patient are admitted to the inpatient hospital ward during the immediate post-operative period and monitored.
 
Post-operative changes in patient comfort vital signs or diagnostics such as liver enzymes will prompt further evaluation.

2	LC Lumi beads	Allergic Response	The preclinical experience does not raise concerns that the radiopaque LC beads produces any known acute allergic response (see Investigator's Brochure).	Patient with known allergy to LC beads or its components will be excluded from the study
3	LC Lumi beads	Endotoxin adverse reaction	The preclinical experience does not raise concerns that the radiopaque LC beads produces any known acute endotoxin response (see Investigator's Brochure).	
Labeled non-pyrogenic Endotoxin testing in animal models proved no change in temperature during an observation period following injection of extracted LC bead LUMI.
 
Acutely febrile patients will be excluded from the procedure as is standard of care

4	LC Bead LUMITM Bead	Genotoxicity, Carcinogenicity, reproductive toxicity	The preclinical experience does not raise concerns that the radiopaque LC beads produces any known genotoxicity, carcinogenotoxic or reproductive toxic adverse events (see Appendix C, Section 0)	Patients who are of reproductive age will be counseled on use of adequate birth control. All women who are of reproductive age and are not sterile or post-menopausal will be tested for pregnancy prior to all imaging.
5	LC Bead LUMITM beads	Systemic or local toxicity	The preclinical experience does not raise concerns that the radiopaque LC beads produces any known acute systemic or local adverse response (see Appendix C, Section 0)	Patient are admitted to the inpatient hospital ward during the immediate post-operative period and monitored. Post-operative changes in patient comfort, physical exam, vital signs or diagnostics such as liver enzymes will prompt further evaluation with imaging and immediate treatment.

Abbreviated Title: RFA + TACE with RO Beads

Version Date: 04/13/2018

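### Routine recording of new adverse events and toxicity evaluability end at 72 hours, before the 1-2 week period the risk table gives for visceral injury from non-target embolization, and no section clearly states the rule for new events from then to day 30

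*Combined protocol and SAP*

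**What the plan says.** Two sections set a 72-hour limit. Section 4.3.1 counts every patient as "evaluable for toxicity from the time of their treatment with LC LUMI radiopaque beads up to 72 hours post completion of treatment". Section 4.1.2 has staff record "Any grade 3 events and higher occurring up to 72 hours post treatment", apart from the events excluded in Section 4.1.3. For milder events it says: "Grade 2 events will be collected and recorded if not resolved before the patient is considered off treatment (72 hours post treatment". Events of grade 1 are not collected.

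The first row of the risk table in Section 9.5, which covers TAE and thermal ablation, lists "Abdominal visceral injury (from non-target embolization, 1-2 weeks following embolization".

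Three other places suggest that collection runs longer:

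- Section 4.1 says that adverse events, "regardless of severity, will be followed for 30 days or until return to baseline or stabilization of event". It then gives a narrower rule for "Serious adverse events that occur more than 30 days after the last administration of investigational agent/intervention": these are recorded and reported if at least possibly related.
- The calendar in Section 3.3 marks adverse events in the 2-month and 12-month columns. Its footnote d reads "See section 4.1.4 for AE data collection and management during the follow up period".
- Section 5.2.2 asks the investigator to tabulate, with no time limit, all serious events, research-related grade 3 and 4 events, and unexpected research-related grade 2 events.

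Section 4.1.3 separately lists acute cholecystitis and acute pancreatitis among anticipated TAE events that are not collected unless the PI judges them unexpected. The Instructions for Use in Appendix C give pancreatitis as an example under non-target embolization.

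**The concern.** The protocol names a harm, says when it occurs, and sets its routine recording window to close before that time. Staff who follow Sections 4.1.2 and 4.3.1 would have no instruction to enter a visceral injury first seen in the second week. Staff who take Section 4.1 as a 30-day collection rule would enter it. If both readings are in use, patients are recorded over different periods, and an event count cannot be tied to one known period of observation.

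Two uses of the data are affected. Section 5.4.1 bases decisions on continuing enrolment on toxicity in patients already treated. Section 7.0 plans descriptive summary tables; it names no toxicity table, but any safety summary built on the 72-hour rule would leave out this injury. The omission also touches a stated interest of the trial. Section 9.1 describes its intent as including safety, and Section 10.1 lists recognition of non-target embolization among the expected benefits of the bead.

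**Working it through.** No sample size or power figure is involved. The check is a comparison of time windows, followed by a trace of one case through the sections.

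**Inputs.** Recording and evaluability window: 72 hours (Sections 4.1.2 and 4.3.1). Timing of the injury: 1-2 weeks (Section 9.5). Longer figure already in the protocol: 30 days (Section 4.1).

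**Arithmetic.**
- 72 / 24 = 3, so the window closes at day 3.
- 1-2 weeks is days 7 to 14, which is 14 - 7 + 1 = 8 days counted inclusively.
- Gap to the start of the period: 7 - 3 = 4 days. Gap to its end: 14 - 3 = 11 days.
- The 72-hour window covers 0 of the 8 days.
- A day-30 window covers 8 of 8, with 30 - 14 = 16 days to spare.
- The interval without one clear rule is 30 - 3 = 27 days.

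**A visceral injury first seen on day 10, section by section.**
- *4.1.2:* not recorded, since day 10 is later than day 3.
- *4.3.1:* outside toxicity evaluability.
- *4.1:* open to two readings. If the 30-day sentence concerns follow-up of events already recorded, it gives no instruction about a new one. If it is a collection rule, the injury is recorded, but the sentence then conflicts with Section 4.1.2 on both window and grade, because it applies whatever the severity.
- *3.3:* the calendar marks adverse events at this time, and footnote d sends the reader to Section 4.1.4. That section covers follow-up, seriousness and causality, and holds no collection rule.
- *5.2.2:* tabulated for the IRB if serious, or if grade 3-4 and at least possibly related to the research.
- *5.2.1 and 5.3:* these cover unanticipated problems and unanticipated serious events. Because the injury is described in the protocol's own risk table, a non-fatal case may meet neither test.
- *5.4.1:* the general duty to report safety concerns to the IRB could apply.
- *4.1.3:* if the injury is acute cholecystitis or pancreatitis, it is not collected unless the PI judges it unexpected. A longer window alone would not change that.

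Some reporting routes therefore exist, but neither 72-hour section tells staff to record the event in the study database.

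**The case against.** The best defence is that 72 hours is a deliberate and consistent choice. It also appears in the stopping rules (Section 3.2.4) and the off-treatment definition (Sections 3.3 and 3.4.1), and it matches the 24-72 hours that the same risk-table row gives for postembolization syndrome. The bead has 510(k) clearance, the procedure is standard care, and the 1-2 week entry is in the procedure row, not in the rows for the bead. A consistent reading is also available: Section 4.1.2 governs routine recording, Sections 4.1 and 4.1.4 govern follow-up of recorded events, and Sections 4.1 and 5.2.2 govern serious events.

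Much of this stands. A reader might infer that all adverse event collection stops at 72 hours, or that a visceral injury in the second week would go unreported. The documents support neither. The calendar marks events to 12 months, the rule for SAEs after day 30 implies that earlier SAEs are recorded, and Section 5.2.2 has no time limit. A reader might also call the 30-day sentence a flat contradiction of Section 4.1.2, but it is one only if read as a collection rule.

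The defence does not supply a sentence telling staff what to record between 72 hours and day 30. The consistent reading has to be assembled from several sections, and footnote d points to one that does not contain the rule. Reporting to the IRB is also not the same as entry in the study database. Expected non-serious grade 2 events, and non-serious grade 3-4 events judged unrelated to the research, have no clear route even on the favourable reading.

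**Conclusion.** The point holds for routine recording and toxicity evaluability. The window in Sections 4.1.2 and 4.3.1 covers none of the 8 days in which the protocol expects this injury, and the other sections suggest a longer window without stating one.

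The consequence is limited. Section 1.1.1 gives imaging as the only objective and Section 7.0 plans descriptive statistics only. A reader who inferred that the primary conclusion is at risk would go beyond the documents. What is affected is the descriptive safety data and the toxicity data behind enrolment decisions. The documents give no rate for this injury, so the number of cases that might be missed cannot be stated.

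The calculation assumes that 1-2 weeks means days 7 to 14 and that both clocks start at the same TAE session. A repeat session would open a new 72-hour window, which could overlap days 7 to 14 by chance but would not cover them by design.

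**What to change.** Reconcile Sections 3.3, 4.1, 4.1.2, 4.1.3, 4.1.4, 4.3.1 and 5.2.2:

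1. State one collection window for new grade 3 or higher events and all SAEs that covers the 1-2 week period. Day 30 after each TAE session is one option, since Section 4.1 already uses that figure. Keep the related-SAE rule thereafter, and say which grades the 30-day sentence covers.
2. Point calendar footnote d to the section that holds this rule.
3. In Section 4.1.3 and the matching sentence of Section 4.3.1, have serious or grade 3 or higher events that may reflect non-target embolization recorded even if anticipated. Acute cholecystitis and pancreatitis are examples.
4. Ascertain these events by chart review within the planned 12-month follow-up. Do not rely on the CT that Section 3.2.3 places within 2 months: calendar footnote a says "All radiological imaging to be performed as clinically indicated and based on the status of the patient", and Section 7.0 accepts patients without follow-up imaging as evaluable.
5. Report 72-hour events separately, and state how many patients were ascertained to the end of the window.

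The stopping rule and the off-treatment definition stay as they are.

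The cost is wording changes plus one chart review per TAE session. The downsides are modest extra abstraction, incomplete ascertainment for patients who leave early under Section 3.4.2, and a safety summary that may look less favourable.

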4.4 TOXICITY CRITERIA

The following adverse event management guidelines are intended to ensure the safety of each patient while on the study. The descriptions and grading scales found in the revised NCI Common Terminology Criteria for Adverse Events (CTCAE) version 4.0 will be utilized for AE reporting. All appropriate treatment areas should have access to a copy of the CTCAE version 4.0. A copy of the CTCAE version 4.0 can be downloaded from the CTEP web site (http://ctep.cancer.gov/protocolDevelopment/electronic_applications/ctc.htm#ctc_40).

5 SAFETY REPORTING REQUIREMENTS/DATA AND SAFETY MONITORING PLAN

5.1 DEFINITIONS

Adverse events and serious adverse events are defined for this study following the standard ISO 14155:2011 for Good Clinical Practice in clinical investigation of medical devices for human subjects.

Abbreviated Title: RFA + TACE with RO Beads

Version Date: 04/13/2018

5.1.1 Adverse Event

Any untoward medical occurrence in a human subject, including any abnormal sign (for example, abnormal physical exam or laboratory finding), symptom, or disease, temporally associated with the subject's participation in research, whether or not considered related to the subject's participation in the research.

5.1.2 Adverse Device Effect

An adverse device effect (ADE) is an AE related to the use of the LC Lumi Radiopaque embolic beads.

Serious Adverse Event (SAE) is an AE that results in the following:

- death
- serious deterioration of the subject's health, leading to
 - life-threatening illness or injury, or
 - permanent impairment of a body structure or function, or
 - in-patient or prolonged hospitalization, or
 - medical or surgical intervention to prevent life-threatening illness or injury or permanent impairment of a body structure or function
- fetal distress, fetal death or a congenital abnormality or birth defect

5.1.3 Serious Adverse Device Effect (SADE)

A serious adverse device effect (SADE) is an ADE that results in any of the consequences characteristic of an SAE. An unanticipated SADE (USADE) is a SADE which is not anticipated by the risk analysis, while an anticipated SADE (ASADE) is a SADE which is anticipated by the risk analysis.

5.1.4 Unanticipated adverse device effect

Defined as any **serious adverse effect** on health or safety or any life-threatening problem or death caused by, or associated with, a device, if that effect, problem, or death was not previously identified in nature, severity, or degree of incidence in the investigational plan or IDE application (including a supplementary plan or application), other unanticipated serious problem associated with a device that relates to the rights, safety and welfare of subjects.

5.1.5 Serious

An Unanticipated Problem or Protocol Deviation is serious if it meets the definition of a Serious Adverse Event or if it compromises the safety, welfare or rights of subjects or others.

5.1.6 Disability

A substantial disruption of a person's ability to conduct normal life functions.

5.1.7 Protocol Deviation (NIH Definition)

Any change, divergence, or departure from the IRB-approved research protocol.

5.1.8 Non-compliance (NIH Definition)

The failure to comply with applicable NIH Human Research Protections Program (HRPP) policies, IRB requirements, or regulatory requirements for the protection of human research subjects.

Abbreviated Title: RFA + TACE with RO Beads

Version Date: 04/13/2018

5.1.9 Unanticipated Problem

Any incident, experience, or outcome that:

- Is unexpected in terms of nature, severity, or frequency in relation to
 - (a) the research risks that are described in the IRB-approved research protocol and informed consent document; Investigator's Brochure or other study documents, and
 - (b) the characteristics of the subject population being studied; **AND**
- Is related or possibly related to participation in the research; **AND**
- Suggests that the research places subjects or others at a *greater risk of harm* (including physical, psychological, economic, or social harm) than was previously known or recognized.

5.2 NCI-IRB AND CLINICAL DIRECTOR REPORTING

5.2.1 NCI-IRB and Clinical Center CD Expedited Reporting of Unanticipated Problems and Deaths

The Protocol PI will report to the NCI-IRB and CC Clinical Director:

- All deaths, except deaths due to progressive disease
- All Serious Protocol Deviations
- All Unanticipated Problems
- All serious non-compliance

Reports must be received within 7 days of PI awareness via iRIS.

5.2.2 NCI-IRB Requirements for PI Reporting at Continuing Review

The protocol PI will report to the NCI-IRB:

1. A summary of all protocol deviations in a tabular format to include the date the deviation occurred, a brief description of the deviation and any corrective action.
2. A summary of any instances of non-compliance
3. A tabular summary of the following adverse events:
 - All Grade 2 **unexpected** events that are possibly, probably or definitely related to the research;
 - All Grade 3 and 4 events that are possibly, probably or definitely related to the research;
 - All Grade 5 events regardless of attribution;
 - All Serious Events regardless of attribution.

NOTE: Grade 1 events are not required to be reported.

5.3 EXPEDITED ADVERSE EVENT REPORTING CRITERIA TO THE MANUFACTURER

The manufacturer will be responsible for all safety reporting related to the use of LC LUMI beads.

The Investigator shall, in accordance with all Applicable Laws and regulations, report all and any unanticipated serious adverse events and/or device malfunctions that are at least possibly related to the investigational device and/or the investigation to Company within twenty four (24) hours

Abbreviated Title: RFA + TACE with RO Beads

Version Date: 04/13/2018

of such adverse events and/or device malfunctions occurring, and to the relevant authority or authorities as shall be required by all such Applicable Laws and regulations (guidance to which may be provided in the Protocol). Investigator shall also provide Company with any other information and assistance as may be requested and/or required by Company to allow Company to comply with its reporting obligations.

All adverse event data will be forwarded to [contact]

5.3.1 Investigator Responsibilities

The Investigator will conduct the study in accordance of the investigational plan, any IRB-imposed conditions, and applicable FDA regulations for protecting the rights, safety and welfare of subjects under the investigator's care, and for obtaining informed consent from each research participant prior to any study related procedures. Investigators are also responsible for maintaining control of the investigational device. The Investigator will also assure monitoring is conducted according to the monitoring plan. IRB approval of the study must be obtained prior to study start and this documentation will be on file. The Investigator will promptly notify the IRB of any significant new information about this investigation.

This clinical study is being conducted at Clinical Center National Institutes of Health. Investigators may determine if potential subjects would be interested in taking part in the investigation but written informed consent will not be obtained from study participants and study participation will not be allowed prior to IRB approval.

The investigational device will only be used on research subjects with the investigator's supervision and will not be used on any person who is not authorized under 21CFR812 to receive it.

